## 2: Specific Aims

Aim 1: Determine whether cellular substrates of differential hormone sensitivity can be identified through creating neuronal progenitors exposed to high dose estradiol (E) and progesterone (P) (100nm each x 3 days) and withdrawal (3 days), with transcriptomic analyses conducted after each treatment.

Aim 2: a) Determine whether transcriptional response in immune-relevant pathways to hormone response and withdrawal in LCLs will, in these long term cultured cells, distinguish women with PPD from controls and, therefore, further implicate differential immune responses in the pathophysiology of PPD; and b) replicate differences in the polycomb repressor complex under both basal and E- and P-stimulated conditions that we previously observed in premenstrual dysphoric disorder (PMDD).

Hypotheses: H1) After exposure to combined E and P, neural progenitor cells from women with PPD will reveal a transcriptional pattern that differs from that in controls; H2) Similar to PMDD, LCLs from women with PPD will demonstrate a differential basal and hormone-stimulated transcriptional response in network and pathways analyses(e.g., Weighted Genome Correlation Network Analysis (WGCNA), Gene Set Enrichment Analysis (GSEA), and Database for Annotation, Visualization and Integrated Discovery (DAVID)).

Experimental Plan: This component of our protocol will build on access to unique samples of women with peripartum mood disorders as follows: 1) to create human-induced pluripotent cells (h-iPSCs) and neuronal progenitor cells whose transcriptional responses to ovarian steroids in vitro will be assessed; and 2) to create lymphoblastoid cell lines (LCLs).

Participants: PPD- Peripheral blood samples will be obtained from women with PPD and control women (matched for age, race and parity) who met the following criteria: 1) participated in the GnRH agonist and E/P replacement-then-withdrawal paradigms conducted at the NIMH IRP; and 2) clearly demonstrated recurrence of depression (in the women with past PPD but not controls) after E/P withdrawal. This group of women with past PPD and controls therefore will represent a highly selected phenotype in which we have demonstrated behavioral ovarian steroid

sensitivity (in past PPD) or the absence of this phenotype (in controls). All women will be otherwise healthy, and medication free.

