Analysis of RNA sequencing data: Reads will be mapped to reference genome Hg19 and normalized. Using edgeR analyses (or other similar platforms), performed in either CLC Bio Workbench 11 or “R” programming environment (or other appropriate environment), differentially expressed genes will be computed between conditions and multiple comparisons will be corrected using the False Discovery Rate (FDR, Benjamini Hochberg) method. For each gene of interest, normalized expression between untreated and hormone treated/withdrawn cell cultures will be further analyzed by 2-way ANOVAs, with hormone condition (i.e., untreated, hormone exposure, hormone withdrawal) as the within-groups factor and diagnostic group (i.e., PPP or PPD versus Controls) as the between-groups factor. The appropriate post-hoc tests will be performed should significant interactions be detected.

Pathway/Network analysis of RNA sequencing data: Pathway/Network analyses (e.g., Gene Set Enrichment Analysis (GSEA)) will be performed on differentially expressed genes to identify significant biological processes, molecular functions and cellular components for samples in the baseline (untreated), E/P-treated condition, and after withdrawal. Additional analyses that could be performed include WGCNA to examine modules of differentially expressed genes between cells from women with PPD and controls under each hormone condition. Finally, we will subject all differentially expressed genes to other bioinformatics tools, such as the Database for Annotation, Visualization and Integrated Discovery (DAVID) to identify functionally related groups and networks, which can help to detect impacted biological, molecular and cellular functional domains.

Validation of RNA-sequencing: mRNA expression analysis using qRT-PCR will be used to quantitate differentially expressed genes at baseline, after E/P exposure, and after E/P withdrawal. TaqMan qRT-PCR assays will be carried out according to the assay developer’s

recommended conditions on a 7900HT Fast Real-Time PCR System. A two-tailed, unpaired Students t-test will be performed for each comparison.

Additional Analyses: it is possible that whole exome sequencing will be performed in these samples, and evaluations of the methylome will be performed on repeated DNA samples across each of the hormonal conditions established in the clinical protocol (i.e., baseline, add-back, withdrawal and follow-up).

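### FDR control is stated only for the between-conditions screen; the gene-level test of a different hormone response in PPD cells has no stated alpha or correction across genes

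*Combined protocol and SAP*

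**What the plan says.** All of this is in Section 1, subsection 2: Specific Aims.

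- **Hypotheses.** Aim 2a asks whether the transcriptional response to hormone and to withdrawal separates PPD from control lines. H2 predicts that "LCLs from women with PPD will demonstrate a differential basal and hormone-stimulated transcriptional response". Aim 1 also speaks of differential hormone sensitivity.
- **Screen** (Analysis of RNA sequencing data). Under edgeR, "differentially expressed genes will be computed between conditions". The multiplicity rule attached to this step reads: "multiple comparisons will be corrected using the False Discovery Rate (FDR, Benjamini Hochberg) method". The FDR level is not given. Nor is it said whether the contrast pools PPD and control cells, is run within each group, or compares the groups.
- **Follow-up.** "For each gene of interest, normalized expression between untreated and hormone treated/withdrawn cell cultures will be further analyzed by 2-way ANOVAs". The model crosses three hormone levels, measured in the same lines, with diagnosis, which varies between lines, so the interaction is one of its terms. What happens next depends on that term: "The appropriate post-hoc tests will be performed should significant interactions be detected". No alpha or correction across genes is given for these tests, and the genes of interest are not defined.
- **Other steps.** Pathway and network analyses run on differentially expressed genes. An optional one is "WGCNA to examine modules of differentially expressed genes between cells from women with PPD and controls under each hormone condition". The qRT-PCR validation uses an unpaired t-test for each comparison.
- **A priori set.** Aim 2b names the polycomb repressor complex, from previous work in premenstrual dysphoric disorder.
- **Sample size.** No number of cell lines, alpha or power is stated for this component.

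**The concern.** If PPD cells respond to estradiol and progesterone differently from control cells, the change between hormone conditions differs by diagnosis. That is an interaction. The plan puts its multiplicity control on another contrast and leaves the interaction to uncorrected gene-by-gene tests.

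Two things are at stake. First, the published list of differential-response genes could contain many chance findings, with no stated bound on their share. Second, depending on how the screen is set up, it may filter out some of the genes the hypothesis is about, or bias the test that follows. The plan leaves that choice open until the data are in hand.

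**Working it through.** The plan gives no figure to reproduce for this component. The power figures in Section 10 belong to the clinical mood analysis. Alpha, donor numbers, gene counts and effect sizes below are assumptions.

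**1. The two contrasts differ.** For one gene, let D_P and D_C be the mean change from untreated to exposed cells in PPD and control donors.

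- A screen pooled over diagnosis tests (D_P + D_C)/2.
- The interaction tests D_P - D_C.

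Benjamini-Hochberg on the first limits the expected share of screened genes with no average hormone effect. It places no limit on false findings for the second.

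**2. Expected false interactions.** With m genes of interest, no true interaction and alpha = 0.05, the expected number is 0.05 x m. If tests are independent, the chance of at least one is 1 - 0.95^m.

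| m | Expected false | Chance of at least one |
|---|---|---|
| 10 | 0.5 | 40.1% |
| 100 | 5 | 99.4% |
| 500 | 25 | about 100% |

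The expected number does not need independence; the last column does.

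**3. Opposite-direction genes under a pooled screen.** Assume 10 donors per group, paired changes with SD 1, and mean change +1 in PPD and -1 in controls.

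- Pooled mean: (1 - 1)/2 = 0. If the screen uses the within-group variance, its null holds and such a gene passes p<0.001 at the nominal 0.1%. If it ignores diagnosis, the group difference enters the error variance and the rate is lower still.
- Interaction: difference 2, standard error sqrt(1/10 + 1/10) = 0.447, noncentrality 2/0.447 = 4.47 on 18 degrees of freedom. The two-sided critical value at 0.001 is 3.92, giving power of about 69.5%.

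**4. Other readings of the screen.** A simulation used 15,000 genes, three conditions, donor SD 1 and residual SD 1. Of these genes, 1,500 had a common hormone effect of 1.5, 300 moved in opposite directions (+1.5 and -1.5) and 300 responded in PPD only. Selection was by Benjamini-Hochberg at 0.05, with t-tests standing in for edgeR, followed by the mixed-ANOVA interaction at 0.05. At 10 donors per group:

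| Screen | Interaction type I error among selected genes without interaction | Share of declared interactions that are false | Opposite-direction genes selected, of 300 |
|---|---|---|---|
| Pooled over diagnosis | 0.049 | 73% | 0.1 |
| Within each diagnosis, lists combined | 0.096 | 25% | 139 |
| PPD versus control under hormone | 0.305 | 1.4% | 227 |

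The pooled screen leaves the per-gene error rate at its nominal level but loses the opposite-direction genes. The group-specific screens find many of them but bias the later test on the same data. The false share is low in the last row because few genes without an interaction pass that screen.

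**5. Testing the interaction directly.** In the same simulation, Benjamini-Hochberg at 0.05 on the interaction for all genes gave a realised FDR of about 4.6% and found 276 of the 300 opposite-direction genes at 10 donors per group. At 5 per group it found about 38, and at 20 about 300, again with FDR near 4.6%.

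**The case against.** The strongest reply is that several harsher conclusions are inference, and that is correct.

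- A reader might infer that opposite-direction genes are never tested. That holds only if the screen pools the diagnostic groups. The text does not say so, and the optional network step implies PPD-versus-control lists within each condition.
- A reader might infer that the genes of interest are simply the screen's hits. The word order suggests this, but the term is undefined and could cover the polycomb set, which was not chosen from these data.
- A reader might infer that selection necessarily inflates the interaction test. It depends on the screen: with pooled selection in the simulation the rate stayed near 5%. Missed genes and a biased test largely arise under different readings and should not both be charged to the plan at once.
- A reader might infer that the ANOVAs are the only test of the hypotheses. H2 also names network and pathway analyses and includes a basal difference, and H1 concerns the pattern after exposure. A PPD-versus-control contrast within a condition can address those parts.

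It is also fair that this is an exploratory laboratory component, separate from the randomised mood comparison.

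What does not fall away is the missing error control. No interaction test is described for the pathway or network steps, and the qRT-PCR t-tests have no interaction term, correction or independent sample.

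**Conclusion.** The point holds in limited form. Under every reading, the only written gene-level test of the diagnosis-by-hormone interaction has no stated alpha and no correction across genes, and FDR control on the screen does not supply one. At an assumed 5% level this means about 5 false interactions per 100 genes without a true one. The loss of opposite-direction genes is conditional on a pooled screen, and the bias of the later test is conditional on a group-specific one. Because the documents give no donor number, FDR level or gene count for this component, the simulated and power figures show direction and rough scale only.

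The change should be made, since mRNA expression is a listed outcome in Section 9. It does not affect the clinical mood analysis.

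**What to change.** In the paragraph on analysis of RNA sequencing data:

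1. Fit one count model to all expressed genes, with donor accounted for and diagnosis-by-condition terms.
2. Test the diagnosis-by-exposure and diagnosis-by-withdrawal contrasts genome-wide, with Benjamini-Hochberg at a stated level, and declare differential-response genes from that list.
3. List the polycomb genes in advance and analyse them as a separate family with its own correction.
4. Keep the per-gene ANOVAs and post-hoc tests to describe genes that pass.
5. Keep basal and within-condition PPD-versus-control contrasts, and the pathway and network analyses, as separate analyses with the contrast behind each gene list stated.

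The cost is a few lines of plan and code on the same sequencing data. The downside is a shorter gene list than uncorrected tests would give.

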h-iPSCs: h-iPSCs will be generated from Sendai virus-transformed T cells (74), a procedure already successfully accomplished in the LNG laboratory, and then differentiated to neuroprogenitor cells (75) (also successfully achieved by LNG), serotonergic (76) (experiments underway in LNG) and dopaminergic neurons (77), (69). Following differentiation, cells will be cultured in a sex steroid-free growth medium which is phenol red-free media to reduce possible exposure to steroid-like activity prior to experimental exposure.

LCLs: EBV-transformed lymphoblastoid cell lines will be made from peripheral blood as described previously (78), and cells from women with PPD and matched controls will be cultured under identical conditions. As for IPSCs, 5 days before hormone exposure, LCLs will be cultured in a sex steroid-free growth medium of phenol red-free media supplemented with 15% knock out serum (KOSR) (estrogen-depleted).

PPD and control cells will be cultured and collected at baseline, after exposure to combined E/P at supraphysiologic doses of 100nm each (in DMSO) for 3 days, and after withdrawal to vehicle only (DMSO alone) or continued E/P treatment for 3 days (to control for latency following initial hormone exposure).

RNA sequencing: Total RNA will be isolated from the cell pellets and then treated with DNase to remove any traces of genomic DNA contamination. Quality assessment of the RNA is done by an Agilent® 2100 Bioanalyzer. Whole-transcriptome RNA sequencing will be performed using an Ion Torrent NGS Sequencer, the Ion Proton. Total RNA will be polyAAA selected and used to prepare cDNA libraries using the Ion Total RNA-Seq Kit v2, barcoded with Ion Xpress™ RNA-Seq Barcodes.

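### The cell-line ANOVA leaves out the continued-hormone cultures grown as its latency control, so within a line withdrawal cannot be told apart from elapsed time (minor)

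*Combined protocol and SAP*

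**What the plan says.** All of this is in the Specific Aims part of the Introduction (combined protocol and SAP).

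- **Aim 1** covers E/P exposure "and withdrawal (3 days), with transcriptomic analyses conducted after each treatment". Aim 2a asks whether the response to hormone and to withdrawal distinguishes PPD lines from control lines.
- **Culture plan.** Cells are collected at baseline and "after exposure to combined E/P at supraphysiologic doses of 100nm each (in DMSO) for 3 days". They are collected again after a further period on vehicle alone or on "continued E/P treatment for 3 days (to control for latency following initial hormone exposure").
- **Analysis of RNA sequencing data.** The edgeR step is general: "differentially expressed genes will be computed between conditions". Genes of interest then go to a two-way ANOVA, diagnosis by condition, "with hormone condition (i.e., untreated, hormone exposure, hormone withdrawal) as the within-groups factor". Follow-up is conditional: "The appropriate post-hoc tests will be performed should significant interactions be detected".
- **Pathway/Network analysis** is done "for samples in the baseline (untreated), E/P-treated condition, and after withdrawal".
- **Validation by qRT-PCR** is to "quantitate differentially expressed genes at baseline, after E/P exposure, and after E/P withdrawal".

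None of these analyses names the continued-E/P samples or a comparison of withdrawal with continued E/P.

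**The concern.** The plan itself treats latency after first exposure as something to control, and it grows cultures for that purpose. Its one explicit within-line model then lists its levels without them. A change seen in the vehicle cultures on day 6 may come from removing the hormones, or simply from being three days later in the sequence, for example through a delayed response to E/P. The three listed levels cannot separate these.

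At stake is the attribution to withdrawal, one of the two treatments in Aim 1 and part of the question in Aim 2a. The same distinction, withdrawal or prolonged exposure, is the protocol's reason for randomising women to withdrawal or continued replacement.

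**Working it through.** **Inputs from the plan.** Untreated is day 0 and exposure ends on day 3. Vehicle and continued E/P both end on day 6 (3 + 3 days; the plan does not print the day). The sub-study has no stated number of lines, power, alpha or effect size, so there is no figure to reproduce.

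**Aliasing.** Let *t* be the effect of elapsed time from day 3 to day 6, *w* the effect of withdrawal, and *c* the effect of three extra days of E/P. Relative to day-3 exposure:

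- withdrawal minus exposure = *w + t*
- continued E/P minus exposure = *t + c*
- vehicle minus continued E/P, same day = *w − c*

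The three-level factor offers only the first, or the comparison with day 0, where exposure also differs. In a design matrix with line effects, exposure, late time, withdrawal and their interactions with diagnosis (taking *c* = 0), the rank is 10 of 12 columns with three levels and 12 of 12 with four. The two missing ranks are withdrawal against time, and diagnosis-by-withdrawal against diagnosis-by-time.

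**Size for the planned interaction.** Assumptions: *n* = 6, 10 or 15 lines per group; no true withdrawal effect; shifts in SDs of the within-line difference (residual variance 0.5 per condition); nominal 5% per gene, ignoring the false discovery rate (FDR) control applied at the edgeR step.

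If elapsed time shifts day 6 by *d* more in one group than in the other, the interaction sum of squares per line index is *d*²/3. So λ = *n*(*d*²/3)/0.5 = 2*nd*²/3, on 2 and 2(2*n* − 2) degrees of freedom. For *n* = 6 and *d* = 0.5, λ = 2 × 6 × 0.25/3 = 1.0, on 2 and 20 df, and the rejection rate is 12%.

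| Difference in time effect by diagnosis | n = 6 | n = 10 | n = 15 |
|---|---|---|---|
| 0 (common shift only) | 5% | 5% | 5% |
| 0.1 SD | 5% | 5% | 6% |
| 0.2 SD | 6% | 7% | 8% |
| 0.3 SD | 7% | 9% | 12% |
| 0.5 SD | 12% | 18% | 26% |
| 1.0 SD | 36% | 59% | 79% |

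Simulation (40,000 runs per scenario) agrees within about 0.4 percentage points for the 0.5 and 1.0 SD rows.

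**Size for a common shift of 0.5 SD.** Withdrawal minus exposure is significant in 35%, 56% and 75%. The three-level condition main effect is significant in 36%, 59% and 79%. But the plan runs post-hoc tests only after a significant interaction, and both are significant together in only 2%, 3% and 4%.

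**The same-day contrast.** Under elapsed-time effects, vehicle minus continued E/P and its interaction with diagnosis stay at about 5%. Under a pure cumulative-E/P effect the position reverses. With a common 0.5 SD shift in the continued cultures alone, the same-day contrast is significant in 35%, 56% and 75%. If that shift differs by 0.5 SD between groups, its interaction is significant in 12%, 19% and 26%. The listed contrast and interaction stay at 5% in those cases.

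**The case against.** A reader might infer that all three analyses listing conditions are confounded, or that the sub-study discards its control. The documents do not support that. The pathway and qRT-PCR sentences fail to name the continued-E/P samples, but they state no contrast between conditions. The qRT-PCR step uses an unpaired t-test, which suits PPD versus control. Such comparisons within one condition are time-matched and unaffected. Both steps work on differentially expressed genes, and neither edgeR nor the optional WGCNA excludes the continued cultures. Only the ANOVA has a closed list.

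A reader might also take the 35–79% rates for a common shift as the plan's error rate. They are rates for comparisons between conditions that the ANOVA reaches only through a significant interaction, and a common shift leaves that interaction at 5%. A biased interaction needs a time effect that differs by diagnosis, for which the documents give no evidence either way. If that effect is a delayed response to E/P, the PPD–control difference is real and falls within the aims; the error is crediting it to withdrawal.

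One could reply that the exposure level was meant to include the continued cultures. The text does not say so, and pooling would not cure the problem: withdrawal minus the mean of day-3 and continued E/P equals *w + t*/2 *− c*/2, so half the time effect remains.

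What stands is the ANOVA point. As written, the model cannot identify a within-line withdrawal effect, or its difference by diagnosis, without assuming away time.

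**Conclusion.** The point holds for the ANOVA, in limited form. With three levels, withdrawal is aliased with elapsed time, and diagnosis-by-withdrawal with diagnosis-by-time. The interaction is misleading only if the time effect differs by diagnosis. The consequence then runs from negligible (5–6% at 0.1 SD) to substantial (36–79% at 1.0 SD), under assumed line numbers and shifts. For the pathway and qRT-PCR steps the gap is only that the control is not named.

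Severity is minor. This is an exploratory sub-study. H1 and H2 concern basal and hormone-exposed cells, Aim 2b concerns basal and stimulated conditions, and the randomised clinical comparison is separate; none is affected. The aliasing follows from the plan's text; the rates are illustrations.

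**What to change.** - Make hormone condition a four-level factor: untreated, E/P for 3 days, E/P then vehicle, E/P continued.
- Pre-specify vehicle minus continued E/P on the same day, and its interaction with diagnosis, as the withdrawal contrast.
- State that this contrast compares stopping with continuing and carries a 3 versus 6 day difference in cumulative E/P. Report withdrawal minus exposure and continued E/P minus exposure beside it. Only two of the three are independent, so together they tell pure mechanisms apart but not every mixture.
- Carry the continued-E/P condition into any pathway or qRT-PCR comparison between conditions.
- Have each line receive both day-6 conditions. The plan's wording leaves this open, and without it the contrast is between lines and loses its pairing.

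**Cost.** Mostly wording, since the cultures are already planned. If the continued cultures were not going to be assayed, it adds at most one assayed condition per line (three to four, +33%). The price in interpretation is that the contrast measures stopping against continuing E/P, not withdrawal free of any difference in exposure.

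### Cell-line study: controls are matched on age, race and parity, but the planned PPD-versus-control tests do not use these factors, so some of those tests will be conservative

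*Combined protocol and SAP*

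**What the plan says.** All of this stands in the Introduction under "2: Specific Aims".

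- **Participants:** samples come from women with PPD and "control women (matched for age, race and parity").
- **LCLs:** the matching is restated: "cells from women with PPD and matched controls will be cultured under identical conditions".
- **Analysis of RNA sequencing data:** the screen is described as "Using edgeR analyses (or other similar platforms"), with Benjamini-Hochberg correction. No design formula, blocking term or covariate is given. The per-gene ANOVA has hormone condition as a within-groups factor and "diagnostic group (i.e., PPP or PPD versus Controls) as the between-groups factor".
- **Validation of RNA-sequencing:** "A two-tailed, unpaired Students t-test will be performed for each comparison". The comparisons are not listed.

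The plan does not say whether matching is by individual pair or by group balance, how many lines are expected, or how much expression variance age, race and parity explain.

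**The concern.** Matching makes the two groups alike on age, race and parity. Expression variation that these factors explain is then shared by both groups and drops out of the difference between group means. A test that ignores the factors still counts that variation in its error term. For affected genes the standard error is overstated, the test runs below its nominal level, and real differences are missed.

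What is exposed is any direct PPD-versus-control contrast within one condition, and the diagnosis main effect. That includes the basal part of H2 and the basal part of Aim 2b, where a PMDD finding is to be replicated. The lines come from a narrowly selected group of women, so numbers may be small and precision is worth having.

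**Working it through.** **Inputs.** There is no planned figure to reproduce: this component states no sample size, effect, SD or power. Everything below is assumed: n lines per group; true difference d = 1 in units of the total between-line SD; two-sided 5% test; R² = share of between-line variance explained by the matching factors (0, 0.1, 0.3, 0.5).

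**1. Standard error.** With groups balanced on the factors, the true variance of the group difference is 2(1 − R²)σ²/n. The unadjusted test estimates about 2σ²/n. The correct SE is therefore √(1 − R²) of the one used: 0.95, 0.84 and 0.71 for R² = 0.1, 0.3 and 0.5.

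**2. True size of the unadjusted test, n = 10.** There are 18 df and the critical value is 2.101. Size ≈ 2·P(T₁₈ > 2.101/√(1 − R²)).
- R² 0.1: threshold 2.215, size 4.0%
- R² 0.3: threshold 2.511, size 2.2%
- R² 0.5: threshold 2.971, size 0.8%

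**3. Power with adjustment, n = 10.** Age, parity and two indicators for a three-level race variable use 4 df, leaving 18 − 4 = 14 (critical value 2.145). Noncentrality is d√(n/2)/√(1 − R²) = 2.236/√(1 − R²) = 2.357, 2.673 and 3.162. Power from the noncentral t is 59%, 70% and 84%.

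**4. Simulation.** Groups matched imperfectly, three-level race, n = 10, d = 1:

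| R² | Size, unadjusted | Power, unadjusted | Power, adjusted |
|---|---|---|---|
| 0.1 | 4.0% | 56% | 59% |
| 0.3 | 2.1% | 57% | 70% |
| 0.5 | 0.9% | 57% | 83% |

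This agrees with the formulas, and it does not depend on individual pairs being kept.

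**5. Cost when the factors explain nothing (R² = 0).** With 3 covariate df, adjusted v unadjusted power is 55% v 56% at n = 10, 45% v 46% at n = 8 and 25% v 28% at n = 5. With 5 covariate df, adjusted power is 54% at n = 10 and 43% at n = 8. With three-level race and imperfect matching at n = 5, it is 22% v 28%.

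**6. Diagnosis-by-hormone interaction.** This is tested on differences between conditions within a line, so a matching-factor effect that is constant across a line's conditions subtracts out. In a simulation with 10 lines per group and an assumed within-line SD of 0.5, size was 4.9%, 5.0% and 5.2%, and power 67%, 67% and 66%, at matched-set correlations of 0, 0.3 and 0.5. Nothing is lost.

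**7. Why not simply pair.** A paired test has n − 1 df instead of 2n − 2. Its confidence interval is narrower only if the within-pair correlation exceeds 1 − (t₂ₙ₋₂/tₙ₋₁)², which is 0.31 with 5 pairs, 0.14 with 10, 0.065 with 20 and 0.03 with 40. Pairing also requires one-to-one matching, which the plan does not state.

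**The case against.** The case on the other side is substantial.

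- **Certainty.** A reader might infer that every group comparison has inflated error bars and loses power. The documents do not support that. It depends on how strongly age, race and parity affect expression in cultured lines, which is not given. At R² = 0.1 adjustment gains about 3 points; the 57% v 83% contrast needs the factors to explain half the variance. This stands, and the claim is limited accordingly.
- **Scope.** A reader might take all of H1, H2 and Aim 2 to be affected. The hormone-response parts rest on the interaction, which largely escapes (step 6). Only a factor that changes the response to hormones would reach it.
- **Silence.** It is tempting to say that edgeR omits the factors and that the t-test compares PPD with controls. The first is unspecified. For the second, the text says only that each comparison is unpaired. The contrasts may include PPD versus control, hormone conditions, or both.
- **Failed lines.** One might argue that failures destroy the balance. Section 4 (Study Procedures, blood samples for IPCs) provides for re-contact and a second sample, so this cannot be presumed.
- **Cost.** Looser matching makes adjustment dearer: one such simulation gave 41% v 46% at 8 lines and 53% v 56% at 10.
- **Purpose.** Matching also serves comparability, and balanced groups deliver that without adjustment. True, but the available precision is still left unused.

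**Conclusion.** The point holds in a limited form. The design matches on three factors that the ANOVA and t-test, as written, do not use, and the edgeR design is unstated. For genes whose expression varies with those factors, single-condition PPD-versus-control contrasts and the diagnosis main effect are conservative. Under the assumed 10 lines per group and 1 SD difference, the power forgone is about 3, 13 and 26 points (59 − 56, 70 − 57, 83 − 57) at 10%, 30% and 50% explained variance. For unrelated genes nothing is forgone. These figures rest on assumed sample size, effect and variance share, and on reasonable balance between the groups.

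The weight is minor. The component is an exploratory laboratory study outside Section 10, and a reader should not infer a risk of false-positive claims from this fault.

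**What to change.** In "2: Specific Aims", under the RNA sequencing analysis and its validation:

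1. State whether matching is one-to-one or by group.
2. Include age, race and parity in the edgeR design for every PPD-versus-control contrast and in the between-groups part of the per-gene ANOVA. Code race in as few categories as the sample allows.
3. For qRT-PCR comparisons of PPD with control lines, replace the unpaired t-test with a linear model of expression on diagnosis plus the same factors.
4. If matching is one-to-one, add a matched-set block as a sensitivity analysis.

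This works for either kind of matching and keeps lines whose matched partner is missing. It is a wording change, and the covariates must already be known in order to match. The price, for genes unrelated to the factors, is about 1 to 3 points of power at 8 to 10 lines per group (more if matching is loose) and about 3 to 6 points at 5 lines. With very few lines the number of covariate terms should therefore be kept small.
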